10.4. Appendix 4: Derived and Transformed Data

10.4.1. General

Multiple Measurements at One Analysis Time Point

 • Mean of the measurements will be calculated and used in any derivation of summary statistics but if listed, all data will be presented. • If there are two values within a time window the value closest to the target day for that window will be used. If values are the same distance from the target then the mean will be taken.
Study Day

 • Calculated as the number of days from date of study drug administration (Dose Date): 
 • Ref Date = Missing → Study Day = Missing • Ref Date < Dose Date → Study Day = Ref Date – Dose Date • Ref Date ≥ Dose Date → Study Day = Ref Date – (Dose Date) + 1
Period Day

 • Calculated as the number of days from treatment date for the respective period: 
 • Ref Date = Missing → Period Day = Missing • Ref Date < Treatment Date → Period Day = Ref Date – Treatment Date • Ref Date ≥ Treatment Date → Period Day = Ref Date – (Treatment Date) + 1

10.4.2. Study Population

Demographics
Age

 • GSK standard IDSL algorithms will be used for calculating age where birth date will be imputed as follows: 
 ○ Only the year of birth will be collected. The date and month will be imputed as '30th June'. • Birth date will be presented in listings as 'YYYY'.
Body Mass Index (BMI)

 • Calculated as Weight (kg) / [Height (m)]²

10.4.3. Safety

Adverse Events
AE'S of Special Interest

 • Cardiovascular (CV) events • Gastrointestinal events • Acetylcholinesterase inhibition events
Adverse Events with Missing Relationship or Missing Serious Indicator

 • If the relationship to study treatment is missing for a treatment-emergent AE, it'll be considered as related to the study treatment. • If the serious indicator "Was event serious?" is missing, the AE will be considered as SAE. • Adverse events with missing relationship or missing serious indicator will be presented as it is in listings but will be treated as related AEs or SAEs in summary tables.

Laboratory Parameters

 • If a laboratory value which is expected to have a numeric value for summary purposes, has a non-detectable level reported in the database, where the numeric value is missing, but typically a character value starting with '<x' or '>x' (or indicated as less than x or greater than x in the comment field) is present, the number of significant digits in the observed values will be used to determine how much to add or subtract in order to impute the corresponding numeric value. 
 ○ Example 1: 2 Significant Digits = '< x ' becomes x - 0.01 ○ Example 2: 1 Significant Digit = '> x' becomes x + 0.1 ○ Example 3: 0 Significant Digits = '< x' becomes x - 1
ECG Parameters
RR Interval

 • IF RR interval (millisecond [msec]) is not provided directly, then RR can be derived as: 
 [1] If QTcB is machine read & QTcF is not provided, then: $RR = \left[\left(\frac{QT}{QTcB} \right)^2 \right] * 1000$ [2] If QTcF is machine read and QTcB is not provided, then: $RR = \left[\left(\frac{QT}{QTcF} \right)^3 \right] * 1000$ • If ECGs are manually read, the RR value preceding the measurement QT interval should be a collected value THEN do not derive. • Machine read values of RR should not be replaced with derived values.
Corrected QT Intervals

 • When not entered directly in the eCRF, corrected QT intervals by Bazett's (QTcB) and Fridericia's (QTcF) formulas will be calculated, in msec, depending on the availability of other measurements. • IF RR interval (msec) is provided then missing QTcB and/or QTcF will be derived as: $QTcB = \frac{QT}{\sqrt{\frac{RR}{1000}}} \qquad QTcF = \frac{QT}{\sqrt[3]{\frac{RR}{1000}}}$

10.5. Appendix 5: Reporting Standards for Missing Data

10.5.1. Premature Withdrawals

Element	Reporting Detail
General	
 Participant study completion (i.e. as specified in the protocol) was defined as completing all phases of the study including the follow-up visit. Withdrawn participants may be replaced in the study. All available data from participants who were withdrawn from the study will be listed and all available planned data will be included in summary tables and figures, unless otherwise specified. Early termination visits will be summarized as early termination visits.

10.5.2. Handling of Missing Data

Element	Reporting Detail
General	
 Missing data occurs when any requested data is not provided, leading to blank fields on the collection instrument: 
 These data will be indicated by the use of a "blank" in participant listing displays. Unless all data for a specific visit are missing in which case the data is excluded from the table. Answers such as "Not applicable" and "Not evaluable" are not considered to be missing data and should be displayed as such.
Outliers	
 Any participants excluded from the summaries and/or statistical analyses will be documented along with the reason for exclusion in the CSR.

10.5.2.1. Handling of Missing and Partial Dates

Element	Reporting Detail
General	
 Partial dates will be displayed as captured in subject listing displays.
Adverse Events	
 The eCRF allows for the possibility of partial dates (i.e., only month and year) to be recorded for AE start and end dates; that is, the day of the month may be missing. In such a case, the following conventions will be applied for calculating the time to onset and the duration of the event: 
 Missing Start Day: First of the month will be used unless this is before the date of study treatment; in this case the study treatment date will be used and hence the event is considered Treatment Emergent as per Appendix 2: Study Phases and Treatment Emergent Adverse Events. Missing Stop Day: Last day of the month will be used, unless this is more than 2 days after the date of study treatment; in this case the study treatment date will be used. Completely missing start or end dates will remain missing, with no imputation applied. Consequently, time to onset and duration of such events will be missing.
Concomitant Medications/ Medical History	
 Partial dates for any concomitant medications recorded in the CRF will be imputed using the following convention: 
 If the partial date is a start date, a '01' will be used for the day and 'Jan' will be used for the month If the partial date is a stop date, a '28/29/30/31' will be used for the day (dependent on the month and year) and 'Dec' will be used for the month. The recorded partial date will be displayed in listings.

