Participants will be randomly assigned to receive either all active treatment (gepotidacin) or placebo for both periods. Approximately 17 participants will be randomized (in a 14:3 ratio) to receive a single dose of gepotidacin 1500 mg (Treatment A) or matching placebo (Treatment B) in Period 1 and gepotidacin 3000 mg (Treatment G) or matching placebo (Treatment H) in Period 2 to obtain 12 evaluable participants on active treatment and 2 evaluable participants on placebo.

The interval for the two 3000-mg doses in Period 2 will be between 6 hours and 12 hours based on the PK and safety results from Part 1.

Participants will participate in 2 treatment periods, and blood and urine samples will be collected for PK analysis of gepotidacin concentrations according to the SoA (see Section 1.3).

For Part 2 only, there may be a 7-day interval between doses in Period 1 and Period 2 to accommodate the adolescent population school schedule. Treatment Period 1 and Treatment Period 2 may be separated by no more than 10 days.

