8.3.1. Time Period and Frequency for Collecting AE and SAE Information

- All SAEs will be collected from the signing of the ICF/assent until the Follow-up Visit at the time points specified in the SoA (see Section [1.3](#)).
- All AEs will be collected from the start of intervention until the Follow-up Visit at the time points specified in the SoA (see Section [1.3](#)).
- Medical occurrences that begin before the start of study intervention but after obtaining informed consent will be recorded on the Medical History/Current Medical Conditions section of eCRF, not the AE section.
- All SAEs will be recorded and reported to the sponsor or designee immediately and under no circumstance should this exceed 24 hours, as indicated in [Appendix 4](#). The investigator will submit any updated SAE data to the sponsor within 24 hours of it being available.

- Investigators are not obligated to actively seek AEs or SAEs after the conclusion of the study participation. However, if the investigator learns of any SAE, including a death, at any time after a participant has been discharged from the study, and he/she considers the event to be reasonably related to the study intervention or study participation, the investigator must promptly notify the sponsor.

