8.3.3. Follow-up of AEs and SAEs

After the initial AE/SAE report, the investigator is required to proactively follow each participant at subsequent visits/contacts. All SAEs, and nonserious AEs of special interest (as defined in Section 2.3.1), will be followed until the event is resolved, stabilized, otherwise explained, or the participant is lost to follow-up (as defined in Section 7.3). Further information on follow-up procedures is given in [Appendix 4](#).

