8.1. Adverse Events Analyses

The severity of AEs and SAEs will be determined by the investigator according to the US National Institute of Allergy and Infectious Diseases Division of Microbiology and Infectious Diseases (DMID) criteria for adult toxicity assessment, with the exception of serum creatinine adolescent laboratory data, which will be assessed using pediatric toxicity criteria. All reported AEs will be coded using MedDRA and summarized by system organ class (SOC) and preferred term (PT).

Adverse event severity is classified as mild (grade = 1), moderate (grade = 2), severe (grade = 3), potentially life threatening (grade = 4) or resulting in death (grade = 5). Adverse events starting after the first dose of study treatment with a missing severity will be classified as severe. If a participant reports an AE more than once within an SOC/PT, the AE with the worst-case severity will be used in the corresponding severity summaries.

Relationship to study treatment, as indicated by the investigator, is classified as “not related” or “related”. Adverse events with a missing relationship to study treatment will be regarded as “related” to study treatment. If a participant reports the same AE more than once within an SOC/PT, the AE with the worst-case relationship to study treatment will be used in the corresponding relationship summaries.

Adverse events analyses including the analysis of AEs, SAEs and other significant AEs will be based on GSK Core Data Standards. All AEs, study drug related AEs, SAEs, and AEs leading to discontinuation of study treatment or withdrawal from study will be provided in separate listings. The relationship between SOC and PT will be listed. Summary tables will be provided by SOC, PT, and maximum grade.

In summary tables where AEs are presented by SOC, PT, and maximum grade, SOCs will be sorted in descending order of the total incidence then alphabetically, PTs will be sorted in descending order of the total incidence then alphabetically within the SOC.

For completely missing or partial missing AE start date or end date, imputation rules will be applied following Section [10.4.1](#).

In addition, a summary of the number and percentage of participants with common AEs, defined as AEs with $\geq 5\%$ incidence in any treatment group, will be presented in descending order of total incidence by PT. The details of the planned displays are provided in [Appendix 10: List of Data Displays](#).

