10.2. Appendix 2: Study Phases and Treatment Emergent Adverse Events

10.2.1. Treatment States

Assessments and events will be classified according to time of occurrence relative to the start and/or stop date of the study treatment for the respective treatment period.

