10.2.1.2. Treatment States for AE Data

Treatment State	Definition
Pre-Treatment	AE Start Date/Time < Study Treatment Start Date/Time
On-Treatment	If AE onset date/time is on or after treatment start date/time & on or before the treatment stop date/time with 2 days lag time Study Treatment Start Date/Time ≤ AE Start Date/Time ≤ Study Treatment Stop Date/Time + 2 Days
Post-Treatment	If AE onset date/time is after the treatment stop date/time with 2 days lag time AE Start Date/Time > Study Treatment Stop Date/Time + 2 days
Onset Time Since First Dose (Days)	If Treatment Start Date/Time > AE Onset Date/Time = AE Onset Date - Treatment Start Date If Treatment Start Date/Time ≤ AE Onset Date/Time = AE Onset Date - Treatment Start Date +1 Missing otherwise
Duration (Days)	AE Resolution Date – AE Onset Date + 1
Drug-related	If relationship is marked 'YES' on eCRF OR value is missing

NOTES:

- If the study treatment stop date is missing then the AE will be considered to be On-Treatment.

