10.10.6. Safety Figures

Safety Tables					
No.	Population	IDSL / TST ID / Example Shell	Title	Programming Notes	Deliverable [Priority]
Adverse Events					
2.1	Safety	AE10	Gastrointestinal Adverse Events of Special Interest Adverse Events	Part 1, Part 2, and combined	SAC [1]
2.2	Safety	SAFE_F1	Plot of Distribution of Cumulative Grades of Acetylcholinesterase-Inhibition Adverse Events of Special Interest	Combine Part 1 and Part 2 in one page	SAC [1]
2.3	Safety	SAFE_F2	Plot of duration and severity of Adverse Events for Individual Participants	Part1 and Part 2	SAC [1]

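### The SAP's rule for a partial AE stop date can place the stop before onset, so AEs starting after the dosing day can get a duration of zero or less

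*SAP*

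**What the plan says.** SAP Section 10.5.2.1 sets conventions for AE dates with a missing day, for use in calculating time to onset and duration. A missing stop day becomes the last day of the month, "unless this is more than 2 days after the date of study treatment; in this case the study treatment date will be used". The companion rule for a missing start day has a floor at the treatment date. The stop-day rule has no matching floor at onset. The same section leaves completely missing AE dates missing and shows partial dates in listings as captured.

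SAP Section 10.2.1.2 defines AE duration in days as "AE Resolution Date – AE Onset Date + 1". SAP Section 10.2.1 classifies events "relative to the start and/or stop date of the study treatment for the respective treatment period". The planned display with AE duration in its title is Safety Figure 2.3 in SAP Section 10.10.6: "Plot of duration and severity of Adverse Events for Individual Participants".

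Protocol Section 8.3.1 sets the collection window: "All AEs will be collected from the start of intervention until the Follow-up Visit". That visit is 7 (±3) days after the last dose. Under Protocol Section 8.3.3, SAEs and AEs of special interest "will be followed until the event is resolved, stabilized, otherwise explained", so a stop date can fall in a later month than the dose.

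On incomplete dates generally, SAP Section 8.1 says: "For completely missing or partial missing AE start date or end date, imputation rules will be applied following Section" 10.4.1. That section covers multiple measurements, Study Day and Period Day, and has no rule for AE dates.

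**The concern.** The replacement moves an imputed stop date back to the dosing date, and an AE can start after that date. Counting both end days, as the SAP's formula does, the shortest possible duration is 1 day, so a derived value of 0 or less is impossible. The moved date can also contradict what the site did record, namely the month in which the event ended.

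Onsets after the dosing day are to be expected, because collection runs to Follow-up. In Part 1 Period 2 the first dose follows a morning meal and the second comes at Hour 12. The 12-hour window for acetylcholinesterase-inhibition events in SAP Section 8.2.1 therefore runs past midnight, and an event in its later hours has k = 1.

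What is at stake is modest: the derived durations behind an individual-participant plot, in a study that randomizes about 17 people per part and has safety among its primary objectives.

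**Working it through.** The documents state no figure on this point, so the check applies the rule by date arithmetic.

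**Inputs**
- Stop-day rule: SAP 10.5.2.1.
- Duration formula: SAP 10.2.1.2.
- Reference date T: taken as the dosing date of the respective period, following SAP 10.2.1. Section 10.5.2.1 does not itself name the period, so this is an assumption.
- Onset: T + k calendar days.
- Part 1 dosing days: 1, 5 and 9 (Protocol Table 2).
- Follow-up: 7 (±3) days after the last dose.

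**How often the replacement applies, given a partial stop date**
- Stop month equal to the dosing month, month of L days, dose on day d: it applies when L − d > 2, that is on L − 3 of L days. This gives 25/28 = 89.3%, 26/29 = 89.7%, 27/30 = 90.0% and 28/31 = 90.3%. Over a year, 365 − 12 × 3 = 329, and 329/365 = 90.1% (leap year 330/366 = 90.2%).
- Stop month later than the dosing month: the end of the next month is at least 28 days after any dosing date, so it always applies.

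**Duration when it applies**

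Duration = T − (T + k) + 1 = 1 − k.

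| k (days from dose to onset) | 0 | 1 | 2 | 3 | 7 | 10 |
|---|---|---|---|---|---|---|
| Derived duration (days) | 1 | 0 | −1 | −2 | −6 | −9 |

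The true duration is at least 1 day, so the derived value is at least k days too short.

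**Lowest value by period**
- Part 1 Periods 1 and 2: the next dose is 4 days later, so k is at most 3, giving 1 − 3 = −2.
- Part 1 Period 3 and Part 2 Period 2: onset up to Follow-up gives 1 − 7 = −6. With the visit window it is 1 − 4 = −3 to 1 − 10 = −9.
- Part 2 Period 1: Protocol Section 4.1 allows a 7-day interval between doses and adds that "Treatment Period 1 and Treatment Period 2 may be separated by no more than 10 days". Only if the 10-day limit also runs from dose to dose is k at most 6 (value −5) to 9 (value −8). If the 10 days run from Period 1 Day 3 to Period 2 Day 1, doses are 12 days apart, k reaches 11 and the value is −10.

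**Two dated examples**
- Dose 5 June, onset 7 June, stop recorded as June. Month-end is 25 days after the dose, so the stop becomes 5 June. Duration = 5 − 7 + 1 = −1.
- Dose 29 June, onset 30 June, stop recorded as July. The stop becomes 29 June, before both the onset and the recorded month. Duration = 29 − 30 + 1 = 0, although the event lasted at least 2 days.

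**What the stop date does not touch**

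On-treatment and treatment-emergent status use the AE start (SAP 10.2.1.2 and 10.2.2), as does the acetylcholinesterase-inhibition window (SAP 8.2.1). Grades are assigned by the investigator.

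**The case against.** **The fault is conditional.** Same-day onset gives 1 day, which is possible. The documents tie cholinergic effects to peak concentration, and Protocol Appendix 7 treats diarrhea during or within 12 hours of dosing as suggestive of a cholinergic effect, so same-day onsets may be common. This stands. For those events the rule may shorten the duration but does not give an impossible value.

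**The 90.1% is not a share of AEs.** A reader might infer that most AE durations are wrong. The documents do not support that: the figure holds only once a stop date is partial, and the rate of partial dates is not given. Part 1 participants are confined from Day −1 to Day 11, and the count could be zero.

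**The reference date could be read as the first dose of the study.** On that reading, an onset on Part 1 Day 19 would get 1 − 18 = −17 days. SAP Section 10.2.1 works by the respective treatment period, so the documents do not support the larger figure.

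**A floor at onset would be enough.** It would remove every zero and negative value. It would still collapse each replaced duration to 1 day when onset is on or after the dosing date, and it would leave stop dates outside the recorded month: the second example would become 30 June for an event recorded as ending in July. This objection does not stand.

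**Section 8.1 could be read as a direct conflict with 10.5.2.1.** A reader might infer that the programmer has two opposite rules for completely missing dates. Section 8.1 supplies no value to apply, because the section it cites has no AE-date rule. The only operative rule is that such dates stay missing. What remains is a loose sentence and a dead cross-reference.

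**Conclusion.** The stop-day rule is wrong as written. When the replacement applies, an AE that starts k days after its period's dosing date gets 1 − k days. That is 1 day for same-day onset, possibly truncated, and 0 or negative for any later onset. The imputed stop can also precede the recorded month. No other section of the SAP repairs this.

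The result takes the respective period's dosing date as the reference. The Part 2 Period 1 value of −8 holds only if the 10-day limit runs from dose to dose.

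Severity is low. Only derived AE duration is affected, and only for AEs with a partial stop date, which are probably few and cannot be counted from the documents. Figure 2.3 is the planned display at risk. Its shell is not in the documents, and no safety table has duration in its title. PK, AE incidence, grades and listed dates are unaffected.

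**What to change.** In SAP Section 10.5.2.1, delete the replacement by the treatment date. Impute a missing stop day as the last day of the recorded month, or as the last contact or AE follow-up date if that falls inside the recorded month. Never set it earlier than the later of AE onset and the first day of the recorded month.

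Applied to the two examples, with assumed last contacts:
- Last contact 12 June: the stop is 12 June, and the duration is 12 − 7 + 1 = 6 days instead of −1.
- Last contact 6 July: the stop is 6 July, and the duration from 30 June is 7 days instead of 0.

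As an editorial item, have SAP Section 8.1 cite 10.5.2.1 in place of 10.4.1, and limit its imputation sentence to partial dates.

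The cost is SAP wording and one date-derivation step, with no new data. The downside is that some durations will be overstated. With no contact date inside the recorded month, an event that ended on 1 July would be given 31 July, which is 30 days too long.

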10.6. Appendix 6: Values of Potential Clinical Importance

10.6.1. ECG

ECG Parameter	Units	Potential Clinically Important Range	
		Lower	Upper
Absolute			
Absolute QTc Interval ^[3]	msec	> 450 ^[1]	
		> 450 ^[2]	≤ 480 ^[2]
		> 480 ^[2]	≤ 500 ^[2]
		> 500 ^[2]	
Absolute PR Interval	msec	< 110 ^[1]	> 220 ^[1]
Absolute QRS Interval	msec	< 75 ^[1]	> 110 ^[1]
Change from Baseline			
Increase from Baseline QTc ^[3]	msec	≤ 30 ^[2]	
	msec	> 30 ^[2]	≤ 60 ^[2]
	msec	> 60 ^[1]	

NOTES:

1. Represent standard ECG values of PCI for HV studies.
2. Represent further subdivisions of ECG values for analysis.
3. Qualifying QTc events, regardless whether QTcB or QTcF, will be captured.

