
Cardiovascular Effects Reversible increase in QT prolongation and a mild increase in heart rate in human participants.
	
In Study BTZ115775 (see GSK Document Number 2015N227098_00 Study ID BTZ115775), the infusion of gepotidacin at a dose of 1000 mg and 1800 mg over 2 hours caused a mild heart rate effect of approximately 6 bpm to 10 bpm and a QT prolongation, measured as $\Delta\Delta\text{QTcF}$, of 12 msec to 22 msec. The QT prolongation evolved during the infusion and was quickly reversed over 2 hours after the end of the infusion. Blood pressure observations were within normal ranges.
 
No changes in QRS or QTc of clinical concern have been seen in the clinic (Phase I studies, including renal impairment and hepatic impairment studies, and Phase II ABSSSI and uUTI [acute cystitis] studies) (see Section 6 in the IB). There were electrocardiographic changes noted in a Phase I hepatic impairment study. The majority of participants with severe hepatic impairment had both predose and maximum postdose ECG parameter QTcB and QTcF values of <450 to \leq479 msec throughout the study. Cardiovascular events reported in the Phase II urogenital gonorrhea study were ECG ST segment elevation and palpitations (1 participant each) in the 1500-mg treatment group and tachycardia (1 participant) in the 3000-mg treatment group.
	
Exclusion criteria, close monitoring of clinical parameters, and AEs will be conducted and stopping criteria will be utilized to mitigate and assess cardiovascular effects.
 
Note: Participants with baseline QTcF interval >450 msec will be excluded.
 
Participant monitoring criteria: Participants experiencing a QTcB and/or QTcF >500 msec and/or a change from baseline in QTc >60 msec (see Section 7.1.2).

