7.1.2. QTc Stopping Criteria

A participant who meets the following bulleted criteria based on triplicate ECG readings will be withdrawn from study treatment:

- Corrected QT (QTc) >500 msec
- Change from baseline of QTc >60 msec

For participants with underlying bundle-branch block, follow the discontinuation criteria listed below:

Baseline QTc with Bundle-Branch Block	Discontinuation QTc with Bundle-Branch Block
<450 msec	>500 msec
450 to 480 msec	≥530 msec

- The *same* QT correction formula *must* be used for *each individual participant* to determine eligibility for and discontinuation from the study. This formula may not be changed or substituted once the participant has been enrolled.

- For example, if a participant is eligible for the protocol based on corrected QTcF, then QTcF must be used for discontinuation of this individual participant as well.
- Once the QT correction formula has been chosen for a participant's eligibility, the *same formula* must continue to be used for that participant *for all QTc data being collected for data analysis*. Safety ECGs and other non-protocol specified ECGs are an exception.
- The QTc should be based on single or averaged QTc values of ECG readings obtained over a brief (e.g., 5 to 10 minute) recording period.

See the SoA (see Section 1.3) for data to be collected at the time of intervention discontinuation and follow-up and for any further evaluations that need to be completed.

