8.2. Safety Assessments

Planned time points for all safety assessments are provided in the SoA (see Section 1.3).

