8.2.3. Electrocardiograms

- Single 12-lead ECG will be obtained as outlined in the SoA (see Section 1.3) using an ECG machine that automatically calculates the heart rate and measures PR, QRS, QT, and QTc intervals. Refer to Section 7.1.2 for QTc withdrawal criteria and additional QTc readings that may be necessary.
- Twelve-lead ECGs will be performed with the participant in a semi-supine position after a rest of at least 10 minutes.
- At each time point at which triplicate ECG are required, 3 individual ECG tracings should be obtained as closely as possible in succession but no more than 2 minutes apart. The full set of triplicates should be completed over a brief (e.g., 5 to 10 minutes) recording period.
- ECG Holter monitoring will be obtained as outlined in the SoA (see Section 1.3). The Holter monitoring data will be sent to GSK and may be analyzed at a later date.

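### Does the SAP leave the QTc tables without a governing QT correction formula?

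*SAP*

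**What the plan says.** SAP 10.6.1 sets cut-points for absolute QTc (450, 480 and 500 msec) and for the increase from baseline (30 and 60 msec). Note 3 is attached to both QTc rows: "Qualifying QTc events, regardless whether QTcB or QTcF, will be captured". Note 2, on the intermediate cut-points, reads "Represent further subdivisions of ECG values for analysis". SAP 10.4.3 gives one formula for QTcB and another for QTcF and does not name either as the analysis variable. In SAP 10.10.5, Tables 2.12 and 2.13 count participants by maximum QTc and by maximum QTc change. Their titles name no formula and their programming notes are empty. SAP 2.1 lists no change concerning QT correction.

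Protocol 7.1.2 says the formula chosen for a participant's eligibility is kept "for all QTc data being collected for data analysis", and adds: "Safety ECGs and other non-protocol specified ECGs are an exception". Eligibility is stated in QTcF in exclusion 21 and again in the note to the cardiovascular row of protocol 2.3.1. Inclusion 3 gives a 450 msec limit without a formula. The monitoring entry in protocol 2.3.1 reads "Participants experiencing a QTcB and/or QTcF >500 msec and/or a change from baseline in QTc >60 msec" and refers to 7.1.2.

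**The concern.** Read together, 7.1.2 and the QTcF entry limit point to QTcF as the analysis formula, whereas note 3 admits both. Because note 2 says the cut-points serve analysis, note 3 could be taken to govern the category tables as well as the listings. An either-formula rule can only move participants up, never down, and a faster heart rate raises QTcB relative to QTcF without any change in QTcF.

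The 12-lead ECG readings are part of the primary safety endpoint, and each part randomizes about 14 participants to active drug and 3 to placebo. One reclassified participant on active drug is 1/14 = 7.1% of the group. If the formulas were merged without a label, a reader could not tell which counts rest on QTcF.

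**Working it through.** The plan states no figure to reproduce. The check has two parts: whether the documents call for pooling, and what pooling would do.

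**Do the documents call for pooling?**

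- SAP 10.4.3 treats QTcB and QTcF as two derived parameters. No variable such as the larger of the two, or either above a limit, is defined.
- Note 3 belongs to the appendix on values of potential clinical importance. Its verb, captured, suits Listings 37 to 39, which flag and list such values.
- Note 2 makes the cut-points available for tables. It does not say that the formulas are merged.
- SAP 8.4 refers ECG displays to the sponsor's core data standards. The shells for Tables 2.12 and 2.13 are not in the documents, so they show neither pooling nor separation.
- The exception in 7.1.2 can be read two ways. Protocol 8.2.3 says "Refer to Section 7.1.2 for QTc withdrawal criteria and additional QTc readings that may be necessary", which suggests unscheduled readings. Protocol 8.2, which covers the scheduled 12-lead ECGs, says "Planned time points for all safety assessments are provided in the SoA", which allows a wider reading. On the wider reading 7.1.2 does not bind these tables. On the narrower one it points to QTcF. Separate QTcF rows serve both.

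**What would pooling do?**

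From SAP 10.4.3, QTcB = QT/(RR/1000)^(1/2) and QTcF = QT/(RR/1000)^(1/3). With RR = 60000/HR, the ratio is QTcB/QTcF = (HR/60)^(1/6). The heart rates below are assumptions.

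| Heart rate (bpm) | QTcB/QTcF | QTcF at which QTcB = 450 msec |
|---|---|---|
| 50 | 0.970 | 463.9 |
| 60 | 1.000 | 450.0 |
| 70 | 1.026 | 438.6 |
| 80 | 1.049 | 428.9 |
| 90 | 1.070 | 420.6 |

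Examples for the absolute limit: 440 × (70/60)^(1/6) = 451.5 msec, and 425 × (90/60)^(1/6) = 454.7 msec. Both exceed 450 under QTcB only.

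For the change from baseline, ΔQTcB = (Q + ΔQ) × ((H + d)/60)^(1/6) − Q × (H/60)^(1/6), where Q is baseline QTcF, ΔQ its rise, H baseline heart rate and d the rise in heart rate. Protocol 2.3.1 gives a heart-rate effect of about 6 to 10 bpm and a placebo-corrected QTcF rise of 12 to 22 msec. The source is intravenous: "the infusion of gepotidacin at a dose of 1000 mg and 1800 mg over 2 hours caused a mild heart rate effect". Assume Q = 400 msec and H = 60 to 70 bpm.

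- ΔQ = 0, d = 6 to 10: ΔQTcB is 5.7 to 10.4 msec. A heart-rate rise of this size does not reach the 30 msec limit by itself.
- ΔQ = 22, d = 10: at H = 60, 422 × (70/60)^(1/6) − 400 = 33.0 msec. At H = 70, 422 × (80/60)^(1/6) − 400 × (70/60)^(1/6) = 32.3 msec. The 30 msec limit is crossed under QTcB only.
- ΔQ = 15, heart rate from 60 to 80 bpm: 415 × (80/60)^(1/6) − 400 = 35.4 msec, so a larger heart-rate rise widens the range.
- To exceed 60 msec under QTcB only with d = 10, QTcF must rise by at least 47.4 msec (grid of Q = 380 to 420 msec, H = 50 to 80 bpm). That is more than twice the 22 msec documented.

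The formulas can therefore disagree about a category, mainly at the 450 and 30 msec limits.

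**The case for a change.** The strongest case for a change is that note 3 sits on rows whose cut-points are marked for analysis, that 7.1.2 reaches expressly to analysis data, that SAP 2.1 is silent, and that the drug's intravenous profile is one in which the formulas can disagree. The remedy would be a few words and labels.

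Part of this stands. The labels are missing, and if note 3 is meant to depart from 7.1.2, SAP 2.1 should have listed it. These are gaps in documentation. They do not make the displays unsound, because the feared harm needs a merged count that no text defines.

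Even with merged counts, participants above 450 msec or with a rise above 60 msec should appear in Listing 39, which covers all ECG values for anyone with a value of potential clinical importance. The 30 msec category may lack that safeguard, since 10.6.1 marks it only as a subdivision for analysis.

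The two-formula wording in protocol 2.3.1 does not decide the issue. It is a monitoring criterion in a risk table and says nothing about SAP displays. Protocol 2.3.1 and 7.1.2 differ and must be reconciled as a matter of participant management. No view is taken here on which criterion is right.

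**Conclusion.** No change to the analysis plan follows. The protocol points to QTcF for analysis, unless its undefined safety-ECG exception covers the scheduled recordings. The SAP derives both corrections separately and adds a broad rule for capturing notable values. A programmer working from this would tabulate QTcF and QTcB as separate labelled parameters, and the QTcF counts would then be the same whether or not the title names a formula.

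The size is minor. The ECG displays are descriptive, no hypothesis is tested, and the number of participants who would change category under pooling cannot be estimated, because the documents give no oral heart-rate effect.

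The conclusion assumes that the unseen shells keep the two formulas apart, as SAP 10.4.3 implies. If they merged them, the counts could only be too high, by an amount that depends on heart rate.
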